7.7.2 Secondary Efficacy Analyses

To Assess the Effect of IL4-R Status on Overall Survival (OS)

The secondary efficacy assessment will be to assess the effect of IL4-R status on overall survival (OS). The median OS with its 80%, 90% and 95% confidence interval will be estimated using the KM method, with IL4-R status as strata.

Survival rates at 6, 9, and 12 months and their exact 95% CI for the OS along with the estimate for median and its 80%, 90% and 95% CI, will be produced using KM method. KM estimates of OS will also be presented graphically at 6, 9 and 12 months for each IL4-R stratum.

Objective Response Rate (ORR)

Objective Response Rate (ORR) is the proportion of subjects who achieved a complete response (CR) or partial response (PR) (by RANO-based criteria using both 2-dimensional and volumetric assessments and which may include the incorporation of advanced imaging modalities based on availability of data) out of all treated subjects. Use of sub-therapeutic doses of Avastin will also be considered in determination of ORR (and will result in a variant of the ORR being calculated). Objective response rate will be summarized using percentages along with two-sided 80%, 90% and 95% Clopper-Pearson CI at scheduled time points. Subjects with baseline assessments but no post-treatment assessments will be excluded from the ORR analysis. In addition, the number and percent of subjects by response CR or PR will be summarized. All derived efficacy variables will be displayed in a data listing.

Progression Free Survival (PFS)

Progression Free Survival (PFS) is measured as the time from catheter placement to the date of confirmed disease progression or death from any cause, whichever occurs first. For subjects who are not known to have died or progressed as of the data-inclusion cut-off date, PFS time will be censored at the time of the last radiologic assessment demonstrating lack of progression or, if during the follow-up period, the time of last contact indicating lack of progression.

PFS= Date of disease progression/death – Date of catheter placement +1

PFS rates at 6, 9, and 12 months and their exact 95% CI for the PFS along with the estimate for median and its 80%, 90% and 95% CI, will be produced using KM method. All derived efficacy variables will be displayed in a data listing. KM estimates of PFS will also be presented graphically at 6, 9 and 12 months.

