7.3.1 Biomarker Analysis including IL4R Expression

Archived tumor tissue specimens from subjects entering the study will be processed by IHC at a CLIA certified laboratory (QualTek Molecular Laboratories, Goleta, CA) for retrospective analysis of IL4R expression to determine if there is a correlation between IL4R expression and tumor response following MDNA55 treatment. Instructions for processing and submitting archived tissue are provided in the Study Reference Guide.

Tissue sections will be graded for IL4R expression by examining staining intensity in a blinded fashion for each specimen using a semi-quantitative scale of 0, 1+, 2+, and 3+ (as well as H-Score). Further quantitative assessment of IL4R staining may include standardized image analysis. Efficacy endpoints (such as PFS, ORR, OS, DOR, DOCB) will be evaluated versus intensity of IL4R expression.

In addition, pre-anesthesia blood sample as well as pre-treatment tumor tissue specimens (from subjects where viable tissue can be harvested at the time of catheter placement) will be processed by Mitra Biotech (Woburn, MA) for exploratory retrospective analysis of the tumor microenvironment by conducting an RNA (ribonucleic acid) based immune profile. Instructions for processing and submitting the blood and biopsy samples are provided in the Study Reference Guide.

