2. OBJECTIVES

Primary Objective

• To assess overall survival (OS).

Secondary Objectives

The secondary objectives of this study are:

- To assess the effect of IL4-R status on overall survival (OS);
- To assess the safety of MDNA55 following CED;
- To determine the objective response rate (ORR) per Response Assessment in Neuro-Oncology (RANO)-based criteria incorporating advanced imaging modalities (conditional on availability of advanced imaging data);
- To assess progression-free survival (PFS).

Exploratory Objectives

The exploratory objectives of this study are:

- To assess the pharmacokinetics (PK) of MDNA55 in peripheral plasma;
- To assess serum anti-MDNA55 antibody titers and, if elevated, determine neutralizing antibody titers;
- To determine the relationship between clinical outcomes and response assessment status by different sets of imaging-based response criteria;
- To perform additional ad hoc efficacy and safety analyses as needed based on the data acquired in this study;
- To assess the performance of the Brainlab catheter during infusion in terms of distribution and convection of the infusate using real time MRI monitoring.

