7.4 Demographics and Baseline Characteristics

Demographic and baseline Subject characteristics will be summarized based on the ITT population and according to the following categories:

- Overall:
- By concentration of MDNA55 administered (1.5, 3, 6, 9 μg/mL);
- By low and high total dose of MDNA55 administered (based on median);
- By IL4R status (IL4R^{High}, IL4R^{Low}).

All demographic and other baseline characteristics will be provided in a listing for ITT Population. Categorical variables will be summarized using frequencies while continuous variables will be summarized using mean, SD, median, minimum, and maximum.

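### The secondary objective asks for the effect of IL4R status on OS, but SAP 7.7.2 plans only separate Kaplan-Meier summaries per IL4R stratum and no between-stratum contrast with an interval

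*SAP*

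**What the plan says.** SAP Section 2 gives the secondary objective as "To assess the effect of IL4-R status on overall survival (OS"); protocol 2.2 has the same objective.

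The analysis is in SAP 7.7.2. It estimates a Kaplan-Meier median, with intervals at three confidence levels (80%, 90%, 95%), "with IL4-R status as strata". Landmark survival proportions for the same three time points as the curves are added, each with an exact 95% interval. For the curves themselves, "KM estimates of OS will also be presented graphically at 6, 9 and 12 months for each IL4-R stratum". SAP 7.7.1.1 adds forest plots of the subgroup estimates and refers to a Section 11 attachment for the list of subgroups. That attachment is not in the text available for this review.

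On measurement, protocol 7.3.1 grades staining on a "semi-quantitative scale of 0, 1+, 2+, and 3+ (as well as H-Score") and allows image analysis as well. SAP 7.4 uses two labels, IL4R High and IL4R Low, without a threshold. SAP 5.4 defines only which subjects have usable tissue.

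On status, protocol 9.2.9 describes the analysis of IL4R expression against response and survival as exploratory and descriptive, and protocol 9.2.2.3 cross-refers to it. Protocol 9.4 tests secondary endpoints in sequence at one-sided 10% and leaves the details to the SAP. The SAP names no IL4R test.

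**The concern.** An effect of status on survival is a comparison between strata. Two medians, each with its own interval, do not give an interval for their difference or ratio, and whether two intervals overlap is a poor substitute. A reader of the planned tables would have to compare High and Low by eye, in a study of 46 to 52 subjects, with no measure of how uncertain that comparison is. A large apparent gap could be over-read as evidence that the target matters, or a real association could be dismissed.

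Two related points need settling at the same time. The rule that turns the IL4R score into High or Low is not visible in the protocol or the SAP body. And the protocol gives two different accounts of whether this analysis is inferential.

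**Working it through.** **What each planned output estimates**

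| Output | Source | Compares strata? |
|---|---|---|
| Median OS with 80/90/95% CI | SAP 7.7.2 | No, one per stratum |
| 6/9/12-month rates with exact 95% CI | SAP 7.7.2 | No, one per stratum |
| Kaplan-Meier curves | SAP 7.7.2 | Visually only |
| Forest plot | SAP 7.7.1.1 | No, per-subgroup estimates |

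Nothing in the list is a contrast.

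**Inputs.** The plan states no power or precision for this objective, so there is no figure of its own to reproduce. The nearest is protocol 9.1: over 80% power for the primary test with 46 subjects, medians of 8 versus 11.5 months, one-sided 10%. With an exponential MLE test and 12 months of follow-up after uniform accrual, this reproduces if accrual lasts about 18 to 24 months or longer (78-82% at 18 months, 80-83% at 24). The accrual length is not stated. With 24 months, about 34 deaths are expected under the alternative. Protocol 9.2 requires more than half of the subjects to have died, so at least 24 of 46. I use 24 to 38 deaths. The High:Low split is not given; I assume 50:50, with 70:30 as a check.

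**Precision of a High-versus-Low hazard ratio.** The standard error of the log hazard ratio is approximately 1/√(d·p·(1−p)), with d deaths and a proportion p in one stratum. The 95% interval is the estimate divided and multiplied by exp(1.96/√(d·p·(1−p))):

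- 38 deaths, 50:50: exp(1.96/√9.5) = 1.89
- 34 deaths, 50:50: exp(1.96/√8.5) = 1.96
- 24 deaths, 50:50: exp(1.96/√6) = 2.23
- 24 deaths, 70:30: exp(1.96/√5.04) = 2.39

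An observed hazard ratio of 0.70 with 34 deaths would have a 95% interval of about 0.36 to 1.37 (0.70/1.96 to 0.70×1.96). At one-sided 10%, the hazard ratio detectable with 80% power is exp(−(1.282+0.842)·2/√d): 0.42 at 24 deaths and 0.50 at 38.

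**What medians alone can show by chance.** Simulated with 46 subjects, no IL4R effect, a 10-month median, 24-month accrual plus 12-month follow-up and a fixed even split, the High median exceeded the Low median by more than 3.5 months (11.5 − 8, the primary design difference) in 21% of trials.

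**Conditional: if a test were added and the cut chosen after survival was seen.** Log-rank simulations with 40 or 46 subjects and no IL4R effect, nominal one-sided 10%:

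- one fixed cut: 10-11%
- best of three cuts: about 22-25%
- best of many cuts between the 25th and 75th percentiles: about 30-35%

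The upper figures for three and many cuts come from a run that assumed a 10-month median OS, 24-month accrual and, for the three grade cuts, 15/25/35/25% at 0, 1+, 2+ and 3+. The lower ones come from a run of 40 subjects over a 36-month study, with 3 and 13 cuts between the 25th and 75th percentiles.

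**The case against.** The protocol synopsis lists the endpoint as median OS by IL4R status, and SAP 4.2 lists OS by IL4R status. SAP 7.7.2 delivers exactly that, with intervals and curves, and protocol 9.2.9 calls the analysis descriptive. On that reading the absence of a test is consistent with the protocol. This much stands: the endpoint is analysed, and a formal test is not owed. It does not remove the gap, because the stated objective is an effect, and a descriptive analysis can still report an effect with an interval.

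A reader might infer that the High/Low cut-off is undefined and can be picked once survival is known. The documents do not support that. The SAP uses High and Low as set labels and places its subgroup definitions in an attachment that could not be examined. The supportable statement is that the cut-off is not in the protocol or the SAP body. Staining is also read by "examining staining intensity in a blinded fashion for each specimen", which protects the score, although not the choice of threshold.

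A reader might also infer that the familywise error rate is already broken. That does not follow. The SAP contains no IL4R test, and under protocol 9.4 one would be reached only after OS and PFS had been rejected.

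**Conclusion.** The point holds as a gap between objective and analysis: no between-stratum estimate with an interval is planned, so the objective as worded is not answered. This does not depend on the attachment. The missing interval would be wide, a factor of about 1.9 to 2.2 either side for 38 down to 24 deaths with an even split, and about 2.4 at 24 deaths with a 70:30 split. The death counts above the minimum and the splits are assumptions. Subjects without usable tissue would reduce the counts further.

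The cut-off is a matter to confirm, not an established defect. The error rates of 22-25% and 30-35% apply only if the attachment fixes no cut, the cut is chosen on the survival data and a test is added. Protocol 9.2.9 and 9.4 do need reconciling, because they leave the status of the analysis unclear.

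The documents also do not show that an adjusted model on the continuous H-score should be the main analysis. The objective names status, a categorical exposure. A model with H-score plus age, KPS and MGMT would have 6 deaths per parameter at 24 deaths (24/4) and 9.5 at 38 (38/4).

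**What to change.** 1. Add to SAP 7.7.2 an unadjusted Cox hazard ratio for IL4R High versus Low in the IL4R population, with 80%, 90% and 95% intervals to match the existing summaries. Describe it as an association, since a single arm cannot separate a prognostic from a predictive effect.
2. Optionally add, as supportive, a model on the continuous H-score and a model adjusted for age, KPS and MGMT.
3. Confirm that the Section 11 attachment fixes one scale and one cut-off. If it does not, write them into the SAP before IL4R results are linked to survival, and label all other cuts exploratory.
4. State whether the analysis is descriptive, as in protocol 9.2.9, or has a place in the 9.4 hierarchy. If the latter, name the test and its position.

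The cost is a few lines of SAP text and one extra model. The sponsor must accept a wide published interval and commit to a single cut-off.

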8.1.3 Objective Response Rate

Objective Response Rate (ORR) is the proportion of subjects who achieved a complete response (CR) or partial response (PR) out of all treated subjects.

According to the modified RANO criteria, a responder is defined by radiographic and clinical criteria (Ellingson *et al.*, 2017a). CR and PR together with Stable Disease (SD) and initial and confirmed Progressive Disease (PD) will be first assessed by radiographic changes in tumor size as determined by conventional MRI and further assessed by use of advanced imaging [e.g. diffusion weighted imaging, perfusion using dynamic susceptibility contrast and/or Tumor Response Assessment Maps (TRAMs), etc.] where available. In addition, deterioration of

neurologic function and increase in steroid use will be used to determine PD provided it is confirmed by advanced imaging and/or biopsy since extended duration of pseudo-progression is frequently observed following immunotherapies such as MDNA55 (Weber *et al.*, 2003a; 2003b; Okada *et al.*, 2015).

For the purpose of study endpoints, Objective Response (OR) status should be confirmed by repeat examination after at least 4 weeks. Patients who receive low-dose bevacizumab (Avastin®) treatment to control edema, a preliminary OR observed at least 4 weeks post-bevacizumab treatment will require a confirmatory OR after at least 4 additional weeks.

Subjects who remain on study following surgical resection / de-bulking with no histological evidence of recurrent tumor will have a best OR of SD following surgery and will continue to be followed by MRI as scheduled until new recurrence or confirmed PD to determine PFS.

Imaging assessment will be carried out using comprehensive imaging guidelines to help identify pseudo-progression where possible.

A blinded central review will be employed to provide independent assessment of response or progression following treatment with MDNA55 according to RANO-based criteria (Wen *et al.*, 2010; Ellingson *et al.*, 2017a) incorporating advanced imaging modalities. To rule out pseudo-progression, advanced imaging modalities and/or biopsy will be utilized.

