9.2.3 Missing Data

All available data will be used, and no efficacy data will be imputed. Procedures for handling missing dates will be described in the statistical analysis plan. For the analyses of response, subjects with baseline assessments but no post-treatment assessments will be counted as non-responders. For time to event variables, patients not known to have experienced an event at the time of analysis will be censored as specified in Section 9.2.5.2.

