9.2.5.2 Secondary Efficacy Variables

Secondary efficacy variables will include OS variants, ORR and PFS.

ORR will be presented as the percentage of subjects with CRs or PRs by the RANO-based criteria, including those incorporating advanced imaging modalities; only confirmed responses will be presented (i.e., those observed on 2 consecutive MRI scans not less than 4 weeks apart and at appropriate interval following discontinuation of bevacizumab if response was not observed prior to use of bevacizumab).

PFS will be summarized using the Kaplan-Meier method. PFS will be assessed using a single sample log-rank test (against historical control) at 10% significance level with null hypothesis of mPFS 4 months and alternative hypothesis of mPFS > 4 months. PFS will be defined as the time

(in weeks) from start of the CED infusion until radiologic or neurologic disease progression or death from any cause. Subjects not know to have died or experienced disease progression at the time of the analysis will be censored at the time of the last radiologic assessment demonstrating lack of progression or, if during the follow-up period, the time of last contact indicating lack of progression.

Graphical displays and incidence estimates will show PFS and OS at 6, 9, and 12 months.

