4.2 Secondary Efficacy Endpoints

- Overall survival by tumor IL4-R status;
 - IL4-R status of tumor will be determined based on archived biopsy from the time of initial diagnosis;
- ORR as determined by an independent central review according to RANO- based criteria
 which may incorporate advanced imaging modalities (e.g. diffusion, perfusion and/or
 TRAMs, conditional upon advanced imaging data being available);
 - ORR is defined as the proportion of subjects who achieved a complete response
 (CR) or partial response (PR) out of all treated subjects;
- PFS, defined as the time from treatment until disease progression or death.

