5.2 Modified Intent to Treat Population (mITT)

A modified ITT population for secondary response analyses (mITT) will comprise all subjects who receive any amount of study drug and have adequate imaging (at least 1 post-treatment scan) and clinical data for the ORR analysis.

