6. STATISTICAL ANALYSIS CONSIDERATIONS

6.1 Handling of Missing Data and Dropout

All available data will be used, and no efficacy data will be imputed. For the analyses of response, subjects with baseline assessments but no post-treatment assessments will be non-evaluable. For time to event variables, subjects not known to have experienced an event at the time of analysis will be censored.

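### The SAP defines ORR over all treated subjects, then excludes those with no post-treatment assessment; the protocol is itself split on how to treat them

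*SAP*

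**What the plan says.** **SAP.** Sections 4.2 and 7.7.2 both define ORR as subjects with CR or PR divided by all those treated. Section 7.7.2 then adds: "Subjects with baseline assessments but no post-treatment assessments will be excluded from the ORR analysis". Section 6.1 gives the matching missing-data rule: "For the analyses of response, subjects with baseline assessments but no post-treatment assessments will be non-evaluable". Section 5.2 sets up an mITT population for response analyses, limited to treated subjects who "have adequate imaging (at least 1 post-treatment scan) and clinical data for the ORR analysis". ORR is to be reported as a percentage with 80%, 90% and 95% Clopper-Pearson intervals.

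**Protocol.** Section 8.1.3 takes the proportion "out of all treated subjects". Section 9.2.3 says that "subjects with baseline assessments but no post-treatment assessments will be counted as non-responders". Section 9.2.5.2 adds that "only confirmed responses will be presented", meaning responses seen on two consecutive scans at least 4 weeks apart.

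The synopsis and section 9.2.2.1, however, define an mITT set for response analyses that needs adequate imaging *or* clinical data. They add a note that patients who die or progress clinically before the first MRI are not evaluable for any response assessment.

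**The concern.** One rate has two denominators within a single SAP paragraph, and the protocol supports each of them in different places. An analyst has to choose, in an open-label trial where the data are visible. Two analysts who both follow the documents could report different ORRs.

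The choice is not neutral. Removing subjects who cannot have responded leaves the numerator as it was and shrinks the denominator, so the rate can only stay the same or rise. In recurrent glioblastoma, subjects with no post-treatment assessment could well include early deaths and deteriorations, which a response rate over all treated subjects would count as failures.

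A smaller matter sits beside this. The SAP's ORR text does not repeat the protocol's requirement that a response be confirmed at least 4 weeks later, although the SAP does ask for confirmed progression in PFS and DOR.

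**Working it through.** **Step 1: the passages side by side.**

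| Place | Treated subject with no post-treatment assessment |
|---|---|
| SAP 4.2 and 7.7.2, definition | in the denominator |
| SAP 7.7.2, later sentence | excluded |
| SAP 6.1 | non-evaluable |
| SAP 5.2 (mITT) | outside the set: a post-treatment scan *and* clinical data are needed |
| Protocol 8.1.3 | in the denominator |
| Protocol 9.2.3 | non-responder |
| Protocol synopsis and 9.2.2.1, note | not evaluable if the patient died or progressed clinically before the first MRI |
| Protocol synopsis and 9.2.2.1 (mITT) | may be inside the set: imaging *or* clinical data suffices |

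SAP 6.1 alone could be read as placing such subjects in a not-evaluable category while keeping them in the denominator. The exclusion sentence in 7.7.2 rules that reading out.

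The two protocol rules could be partly squared by applying the note to early deaths and clinical progressions, and 9.2.3 to everyone else with no assessment. That would still conflict with 8.1.3. It would also count a withdrawal as a failure while leaving out a death. The SAP rule goes further than the note, because it excludes unassessed subjects whatever the reason.

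**Step 2: the effect on the estimate.** Let N be the number treated, r the responders and k the treated subjects with no post-treatment assessment.

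- All treated subjects, unassessed as non-responders: r/N
- SAP exclusion rule: r/(N−k)
- Ratio: N/(N−k), which exceeds 1 whenever k > 0 and r > 0, and is never below 1

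**Step 3: numbers.** The plan gives no expected ORR, no ORR null value and no expected k, so it has no figure to reproduce. Assumptions: N = 52, the approximate enrolment in protocol 4.1, taken as all treated; k from 0 to 6; r = 5 or 10 for illustration.

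| k | N/(N−k) | r = 5 | r = 10 |
|---|---|---|---|
| 0 | 52/52 = 1.000 | 9.6% | 19.2% |
| 1 | 52/51 = 1.020 | 9.8% | 19.6% |
| 3 | 52/49 = 1.061 | 10.2% | 20.4% |
| 4 | 52/48 = 1.083 | 10.4% | 20.8% |
| 6 | 52/46 = 1.130 | 10.9% | 21.7% |

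At k = 6 the rate rises by 1.3 percentage points for r = 5 and by 2.5 for r = 10. The 95% Clopper-Pearson interval for r = 10 moves from 9.6–32.5% (n = 52) to 10.9–36.4% (n = 46).

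**Step 4: is that range of k reasonable?** As a guide to scale only, use exponential survival with the medians of protocol 9.1 and 30.4375 days per month. The expected deaths among 52 before Day 30 are 52 × [1 − exp(−(ln 2/m) × 30/30.4375)].

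- m = 8 months: 52 × 0.082 = 4.3
- m = 11.5 months: 52 × 0.058 = 3.0

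The life-expectancy criterion would lower these counts. Clinical progression or withdrawal before the first assessment would raise k.

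**Step 5: which scan counts?** Protocol Table 6 schedules an MRI within 4 hours of the end of infusion, and another at 18 to 30 hours that includes tumor dimensions and volume. Follow-up MRIs begin at Day 30. Neither document says which of these is the first post-treatment scan. If the 18 to 30 hour scan qualifies, k is near zero and so is the inflation. If only Day 30 onward qualifies, early deaths drop out.

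**The case against.** The strongest reply is that the SAP did not invent this rule. The protocol sets up an mITT population for response and says outright that early deaths and clinical progressions before the first MRI are not evaluable. SAP 5.2 and 6.1 follow that line. This stands. A reader might infer that the SAP reverses a clear protocol rule, but the documents do not support that, because the protocol is on both sides. It also means that an edit to the SAP alone would only exchange one conflict for another.

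Second, the effect may be negligible. The number unassessed is unknown, the 18 to 30 hour scan may qualify, and protocol 7.5.4 generally asks subjects who stop early for the Day 360 procedures, or uses a recent scan or visit instead. This stands too. A reader might infer that ORR *is* inflated, or that those excluded are mainly treatment failures. The documents contain no data to show either.

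Third, ORR is a secondary endpoint, moved there because imaging was judged confounded. Protocol 9.4 puts the secondary endpoints in a testing hierarchy, but no null value for ORR is given and SAP 7.7.2 plans only estimates and intervals. A reader might infer that a formal ORR test or a comparison with historical rates is compromised, but neither document specifies one.

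Fourth, the SAP's silence on confirmation is an omission. It does not contradict the protocol's rule, and the SAP is written for protocol version 6.1. It should not be read as a decision to count unconfirmed responses.

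None of these replies removes the conflict inside SAP 7.7.2, or the one between SAP 7.7.2 and protocol 9.2.3.

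**Conclusion.** The ORR rule is wrong as written, with moderate severity. The SAP's definition and its exclusion sentence give different denominators, and the protocol supports both. The direction is certain: if at least one treated subject is unassessed and at least one responds, the SAP rule raises ORR by the factor N/(N−k). The size is conditional. With an assumed 52 treated and 0 to 6 unassessed, the relative inflation is 0 to 13%, or at most about 2.5 percentage points for an ORR near 20%. The illustrative r and k are assumptions. The primary overall survival analysis uses all treated subjects and is not touched.

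**What to change.** 1. In SAP 6.1 and 7.7.2, replace the conflicting sentences with one rule: ORR is the number of subjects with CR or PR, confirmed at least 4 weeks apart as in protocol 8.1.3 and 9.2.5.2, divided by all treated (ITT) subjects. Subjects with no post-treatment assessment count as non-responders.
2. Reconcile the not-evaluable note and the mITT wording in the protocol synopsis and 9.2.2.1 with that rule. Settle the *or* in the protocol's mITT definition against the *and* in SAP 5.2.
3. State which scan is the first that qualifies as a post-treatment response assessment.
4. Report ORR on the mITT denominator as a labelled sensitivity analysis, with the number excluded and the reason for each.

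The cost is wording in the SAP and a matching clarification of the protocol. No new data are needed. The headline ORR may be slightly lower than under the exclusion rule, and is the same if nobody is unassessed.
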